Table 3	AE Reporting Timeframes and Process for Investigators and Vendors	41

LIST OF ABBREVIATIONS

AE	Adverse Event	
ALT	Alanine Transaminase	
ALT	Alanine Transaminase Aspartate Transaminase	
ARO	Academic Research Organization	
BD	Business Day	
BNP	Brain Natriuretic Peptide	
CD	· · · · · · · · · · · · · · · · · · ·	
	Calendar Day	
CEP	Cyclic Guanosine Monophosphate	
CFR	Code of Federal Regulations	
CHD	Congenital Heart Disease	
CRF	Case Report Form	
CRO	Contract Research Organization	
CTEPH	Chronic Thromboembolic Pulmonary Hypertension	
DMP	Data Management Plan	
EMA	European Medicine Agency	
EQ5D	EuroQoL questionnaire	
ERA	Endothelin receptor antagonist	
FDA	Food and Drug Administration	
FPE	First Patient Enrolled	
GCP	Good Clinical Practice	
GPP	Good Publication Practice	
GVP	Good Pharmacovigilance Practice	
ICH	International Conference of Harmonization	
IEC	Independent Ethics Committee	
INN	International Nonproprietary Name	
MedDRA	Medical Dictionary for Regulatory Activities	
MCV	Mean Corpuscular Volume	
MCH	Mean Corpuscular Hemoglobin	
MCHC	Mean Corpuscular Hemoglobin Concentration	
N/A	Not Applicable	
NMPA	National Medical Products Administration	
NO	Nitric Oxide	
NT-proBNP	N-terminal pro Brain Natiruretic Peptide	
WHO functional class	WHO Functional Class	
OM	Operating Manual	
OS	Observational Study	
РАН	Pulmonary Arterial Hypertension	
PAS	Post-Authorization Study	
PASS	Post-Authorization Safety Study	
PEA		
PH		
PSUR		
PV		
PH PSUR	Pulmonary Endarterectomy Pulmonary Hypertension Periodic Safety Update Report Pharmacovigilance	

MK-4836-001-01 FINAL PROTOCOL

SAE	Serious Adverse Event	
SAP	Statistical Analysis Plan	
STROBE	Strengthening the Reporting of Observational Studies	
	in Epidemiology	
VAS	Visual Analogue Scale	
VKA	Vitamin K Antagonists	
6MWT	6-Minute Walk Test	

MK-4836-001-01 FINAL PROTOCOL

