6.1.3 Strengths of Study Design

In this therapeutic area a multicenter exposure registry with a mix of patients previously enrolled in two Bayer Phase III clinical trials with riociguat and patients newly starting Adempas[®] allows for a structured prospective documentation of long-term data on safety, clinical effect, and information on how Adempas[®] is used by PH experts. As Adempas[®] is the first sGC-stimulator in clinical use and all available clinical data in Chinese patients derive from well-defined clinical studies, this registry may collect additional data on important potential safety risks, drug interactions and missing information.

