6.3.2 Variables to Determine the Secondary Endpoints

The outcome variables for secondary objectives are:

- AE and SAE in the different PH indications (PAH, CTEPH)
- Adverse events of interest
 - o Symptomatic Hypotension (date BP measurement, symptoms)
 - o Haemoptysis and pulmonary haemorrhage (serious and non-serious).

Specific information regarding relevant history, current condition, diagnostics, treatment, specific lab values and outcome to be documented in a specific CRF section in case AE/SAE of interest occurred

- Measurements of clinical effect
 - o 6-minute walk test
 - o WHO FC
 - o Borg dyspnoea index
 - o EQ5D VAS
 - o Haemodynamic parameters from right heart catheter measurement
 - o Biomarkers
- Resource use

o Hospitalization (due to PH or other reason, emergency admission, intensive care unit, number of days)

- o Outpatient visits at PH centre
- o Home care (nurse, days per week, hours per day)
- o Drug use, including switch or interruption or discontinuation of Adempas[®] and associated reason

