6.3.16 Prior and Concomitant Medication

All medication taken before study start (initiated and stopped before study start) is termed prior medication. All medication taken in addition (either initiated before study start or during the study) is termed concomitant medication.

Prior and concomitant medication meeting the criteria listed below are considered to be relevant and must be documented:

- PH/PAH-specific therapy
 - o Adempas®
 - o ERA
 - Bosentan
 - Ambrisentan

o PDE-5 inhibitors (physician will be alerted that the combination of PDE5 inhibitors with Adempas[®] is contraindicated)

o Nitrates or nitric oxide donors (physician will be alerted that the combination of PDE5 inhibitors with Adempas[®] is contraindicated)

- o Prostacyclins
 - Epoprostenol
 - Treprostinil
 - Iloprost

- Beraprost
- o Other specific targeted therapy: calcium channel blocker
- o Oral anticoagulation
 - Vitamin K antagonists
 - Other
- Other medications (only CHD: other cardiovascular drugs, antiplatelets)

Information to be documented includes:

- Trade name and INN
- Start and stop date
- Date of dose change, switch or addition of a specific drug/Adempas[®]
- Reason for change (lack of efficacy or tolerability, patient's request, administrative)
- Dose
- Unit
- Frequency
- Administration mode
- Indication

Additional information on Adempas[®] to be documented includes:

- Individual dose after initial dose adjustment period
- BP before the 1st administration

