6.7.3 Analysis of Primary Outcome(s)

The main goal of this national registry is to assess the long-term safety of Adempas[®] in real life clinical use. Incidences of treatment-emergent adverse events, serious adverse events and all-cause mortality will be calculated, including adverse events of interest. An adverse event is considered as treatment-emergent when it has started or worsened after first dose of study medication after enrollment up to 2 days after end of treatment with study medication.

For the events, the 'raw' incidence proportion (regardless of the time each patient is treated), i.e. number of patients with events divided by the number of treated patients, will be presented as well as incidence rates, i.e. number of patients with events divided by the cumulative person-time on treatment (person-years) separately for incident and prevalent patients.

If the patient numbers allow, the statistics will be calculated for Adempas[®] and stratified for medically relevant subgroups, e.g.:

- Age
- Gender

MK-4836-001-01 FINAL PROTOCOL

- Aetiology (Nice Classification of PH)
- Hepatic impairment at baseline
- Renal impairment at baseline
- WHO functional class group at baseline
- According to e.g. 6 MWD thresholds \geq 380 m versus < 380 m at baseline
- Type of PH pre-treatment
- Concomitant medication use
- Systolic blood pressure at baseline
- Dosing level

A comprehensive list of medically relevant subgroups will be added to the SAP.

Tables which show the incidence proportion of adverse events overall and by MedDRA preferred term within the primary SOC will also be presented. Incidences of adverse events and serious adverse events starting more than 2 days after end of treatment will be tabulated separately.

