9.2.2 Adverse Reaction (AR); also referred to as Adverse Drug Reaction (ADR)

An AE which has a causal relationship with the product, that is, a causal relationship between the product and the adverse event is at least a reasonable possibility. An Adverse Reaction (AR) is any AE judged as having a reasonable suspected causal relationship to Adempas[®].

Causal relationship: The assessment of the causal relationship between an AE and the administration of treatment is a clinical decision based on all available information at the time of the completion of the CRF. The assessment is based on the question whether there was a "reasonable causal relationship" to the study treatment in question. Possible answers are "yes" or "no".

An assessment of "no" would include:

- The existence of a clear alternative explanation (e.g. mechanical bleeding at surgical site)
- Non-plausibility (e.g. the subject is struck by an automobile when there is no indication that the drug caused disorientation that may have caused the event; cancer developing a few days after the first drug administration)

An assessment of "yes" indicates that there is a reasonable suspicion that the AE is associated with the use of the study treatment. Factors to be considered in assessing the relationship of the AE to study treatment include:

- The temporal sequence from drug administration: The event should occur after the drug is given The length of time from drug exposure to event should be evaluated in the clinical context of the event
- Recovery on drug discontinuation (de-challenge), recurrence on drug reintroduction (re-challenge): Subject's response after de-challenge or subjects response after re-challenge should be considered in the view of the usual clinical course of the event in question
- Underlying, concomitant, intercurrent diseases: Each event should be evaluated in the context of the natural history and course of the disease being treated and any other disease the subject may have
- Concomitant medication or treatment: The other drugs the subject is taking or the treatment the subject receives should be examined to determine whether any of them may be suspected to cause the event in question
- The pharmacology and pharmacokinetics of the study treatment: The pharmacokinetic properties (absorption, distribution, metabolism and excretion) of the study treatment, coupled with the individual subject's pharmacodynamics should be considered.

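### Antiplatelets and other cardiovascular drugs are required in the CRF only for patients with congenital heart disease, so description of hypotension and lung bleeding by co-medication is incomplete for these two classes in all other patients

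*Protocol*

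**What the plan says.** Section 6.3.16 sets the rule for medication data: "Prior and concomitant medication meeting the criteria listed below are considered to be relevant and must be documented". The list names PH-specific therapy (Adempas, endothelin receptor antagonists, PDE-5 inhibitors, nitrates or nitric oxide donors, prostacyclins, calcium channel blockers), then "Oral anticoagulation" (vitamin K antagonists and other), and ends with "Other medications (only CHD: other cardiovascular drugs, antiplatelets". The list of abbreviations expands CHD as "Congenital Heart Disease". For each listed drug the dose, start and stop dates and indication are recorded, among other items.

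Four other places bear on this:
- Section 6.3.2 names the adverse events of interest: symptomatic hypotension, and "Haemoptysis and pulmonary haemorrhage (serious and non-serious"). It adds a specific CRF section on history, diagnostics, treatment and outcome, to be completed when such an event has occurred.
- Section 6.7.3 plans to stratify the safety incidences by medically relevant subgroups if patient numbers allow. One of its examples is "Concomitant medication use".
- Section 6.1.3, on the strengths of the design, says that "this registry may collect additional data on important potential safety risks, drug interactions and missing information".
- Section 9.2.2, on causality, says of concomitant medication: "The other drugs the subject is taking or the treatment the subject receives should be examined".

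**The concern.** The registry singles out hypotension and lung bleeding for extra attention. Other blood-pressure-lowering drugs are an obvious alternative contributor to the first, and antiplatelets to the second. These are the classes whose recording stops at CHD. The protocol names idiopathic, heritable and connective-tissue-disease PAH as the aetiologies of the confirmatory trial (section 4) and enrols CTEPH as well; none of these groups falls under the CHD item.

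What is at stake is a description: how often the events of interest occur in patients with and without these drugs. This concerns what is collected and not how it is analysed, so no statistical analysis plan can recover it once data collection has ended.

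**Working it through.** The protocol gives no figure to reproduce. The analysis is descriptive (6.7.1), with no alpha, power or margin. The check is a comparison of passages, followed by an illustration of precision.

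**1. Is the list closed?** Section 6.3.16 first defines concomitant medication broadly, as anything taken in addition, but then requires documentation only of what meets the listed criteria. The visit schedule in 6.2.8 refers to relevant prior and concomitant medication, and Table 1 has one row for concomitant medication. Neither widens the list. Section 6.3.15 restricts a set of laboratory tests to CHD patients in the same way, so the restriction looks deliberate. The bracket could be read as qualifying only the two named groups within a general item on other medications. On that reading too, those two groups remain limited to CHD.

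**2. What is recorded in whom?**

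| Class | CHD patients | CTEPH and non-CHD PAH |
|---|---|---|
| Oral anticoagulants | required | required |
| Calcium channel blockers | required | required |
| Nitrates / nitric oxide donors, PDE-5 inhibitors | required | required |
| Endothelin receptor antagonists, prostacyclins | required | required |
| Antiplatelets | required | not required |
| Other cardiovascular drugs | required | not required |

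**3. Does the event-specific CRF section fill the last two rows?** No. It is completed only after an event of interest. At best it gives the number of patients with the event who took the drug. The incidence proportion in 6.7.3 is patients with events divided by treated patients, so a split by drug use also needs the users and non-users among patients without an event. Those counts are not collected outside CHD. The word treatment in that section may also mean treatment of the event.

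**4. What follows for 6.7.3?** The stratum can be formed for the first four rows in all patients. For the last two it can be formed only within CHD.

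**5. How much could the missing table show?** All inputs here except the 80 patients are assumptions. Take an overall risk of symptomatic hypotension of 10% (80 × 0.10 = 8 events), a share p of 20–40% on another blood-pressure-lowering drug, and a risk ratio RR of 2–3. For simplicity all 80 patients are taken as affected, although the CHD share is not stated.

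Risk without the drug = 0.10 / (1 − p + p × RR); risk with it = that value × RR.

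- Without the drug: from 0.10 / (0.6 + 0.4 × 3) = 0.10 / 1.8 = 5.6% to 0.10 / (0.8 + 0.2 × 2) = 0.10 / 1.2 = 8.3%.
- With the drug: from 0.10 / (0.6 + 0.4 × 2) × 2 = 14.3% to 0.10 / (0.8 + 0.2 × 3) × 3 = 21.4%.

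Take p = 30% and RR = 2. There are 24 users and 56 non-users. Expected events are 24 × 0.154 = 3.7 and 56 × 0.077 = 4.3, so about 4/24 and 4/56. The exact 95% intervals are 5–37% and 2–17%. Across all combinations of p = 20, 30, 40% and RR = 2, 3, with counts rounded to whole patients, the intervals overlap and the two-sided Fisher p-value lies between 0.12 and 0.26.

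**The case against.** The strongest reply is that much relevant co-medication is recorded in everyone. Bleeding can be tabulated by anticoagulant use, with INR where available for patients on vitamin K antagonists (6.3.15). Hypotension can be tabulated by calcium channel blocker, endothelin receptor antagonist or prostacyclin use. A reader might infer from 6.3.16 that outside CHD these events cannot be separated from co-medication at all. The list itself refutes that.

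A reader might also infer that drug-interaction data cannot be produced. That does not follow either. Interactions with the recorded classes can be described, and suspected drug interaction is a listed reason for discontinuation or withdrawal (6.2.8). Section 6.1.3 says only that the registry may collect such data; it is neither an objective nor an endpoint.

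Nor is causality assessment disabled. Section 9.2.2 obliges the investigator to consider the patient's other drugs whether or not the CRF lists them, and further information can be requested (8.4, 9.1.2).

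The stratum in 6.7.3 is an example, conditional on numbers, and names no drug class. At about 8 events, the added table could not distinguish the groups statistically.

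All of this stands, and it limits the point. It does not remove it: two classes pertinent to the events of interest lack exposure data outside CHD, and section 6.9 does not list this among the limitations.

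**Conclusion.** The point holds as a limited gap in data collection. In CTEPH and non-CHD PAH, the protocol does not require antiplatelets or other cardiovascular drugs to be documented. Stratification by concomitant medication and any description of interactions are therefore incomplete for these two classes, for symptomatic hypotension and for haemoptysis or pulmonary haemorrhage. The six classes recorded in everyone are not affected, and neither are the overall incidences of AEs, SAEs, events of interest or death.

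The size cannot be taken from the documents, which state neither the CHD share, nor the use of these drugs, nor the event risks. The 5.6–8.3% versus 14.3–21.4% contrast is an illustration on assumed inputs and should not be read as a forecast. The same assumptions show that about 8 events in 80 patients would leave wide, overlapping intervals. The conclusion rests on reading 6.3.16 as a closed list, which its wording supports and no other section contradicts.

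**What to change.** In 6.3.16, delete the restriction to CHD for these two groups. Require cardiovascular drugs (including blood-pressure-lowering drugs) and antiplatelets to be recorded for all patients from routine records, at the initial and follow-up visits, with the same items as the other listed drugs. Under 6.7.3, describe the events of interest by baseline use of these classes, as counts and proportions with a statement that the comparison is descriptive only. If the sponsor prefers to keep the restriction, 6.9 should state the gap.

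The cost is a change of protocol and eCRF wording and a few extra medication rows per patient, for 80 patients in a country with approximately 10 active PH centres (6.5). No visit, test or procedure is added. The resulting subgroup figures will be imprecise at this sample size.

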6.4 Data Sources

The investigator collects current and historic patient data (demographic and clinical characteristics) from medical records if available. Likewise, the investigator collects treatment related data during visits that take place in routine practice. Each patient is identified by a unique central patient identification code, which is only used for study purposes. For the duration of the study and afterwards, only the patient's investigator is able to identify the patient based on the patient identification code.

6.5 Study Size

Per regulatory commitment, study accrual will continue until at least 80 patients are enrolled, including a reasonable number of newly treated Adempas[®] patients. The study will allow to prospectively collect data on the safety and clinical effect of Adempas[®] treatment in real-life clinical practice in China.

The sample size rationale is listed below.

MK-4836-001-01 FINAL PROTOCOL

- Epidemiology of PH indicates a low incidence (incidence of PAH: 2-8/million/y; incidence of CTEPH in Great Britain: 12.3-16.6/million/y; no incidence data available in China).
- Enrolment period: The enrollment period available for this study is limited to <1.5 years because commercial drug will not be available for 1 year after approval, patients will be observed for around 1 year, and time is needed for data clean-up and analysis to complete/submit the study report with the renewal submission ~12 months prior to license expiry".
- Limited number of PH centres (approximately 10 active PH centres) in China.
- Therapeutic environment: Adempas[®] is not the only option for PAH treatment.
- Chinese patient number enrolled in the CTEPH and PAH pivotal studies (109 patients were enrolled in over 2 years; this corresponds to 81 patients in 1.5 years).

6.6 Data Management

An Academic Research Organization (ARO) will be selected and assigned for EDC system development. The CRF will be part of the EDC system which allows documentation of all outcome variables and covariates by all participating sites in a standardized way. Information on the EDC system will be available upon request. Detailed information on data management, including procedures for data collection, retrieval and preparation will be provided in the Data Management Plan (DMP), which will be available upon request.

For information on quality control, refer to Section 6.7.7.

6.7 Data Analysis

6.7.1 Statistical Considerations

Statistical analyses of this study will be descriptive.

All background variables and outcome parameters will be analyzed descriptively with appropriate statistical methods: categorical variables by frequency tables (absolute and relative frequencies) and continuous variables by summary statistics (i.e. mean, standard deviation, minimum, median, quartiles and maximum). Continuous variables will also be described by absolute value and as change from baseline per analysis time point, if applicable.

All analyses will be performed for the total study population (overall analysis) and separately for PH subtype and relevant subgroups, (e.g., age, gender, incident and prevalent patients, functional class at baseline, titrated dose), if patient numbers are sufficient. Prevalent patients are here defined as patients already on treatment when enrolled in the study, whereas incident patients will be patients newly starting Adempas[®].

Patients receiving at least one dose of Adempas[®] will be included in the analysis. Whenever reasonable, data will be stratified by subgroups (e.g. age, gender).

All therapies documented will be coded using the World Health Organization – Drug Dictionary (WHO-DD). Medical history, any diseases and AEs will be coded using the latest Medical Dictionary for Regulatory Activities (MedDRA) version.

All statistical details including calculated variables and proposed format and content of tables will be detailed in the Statistical Analysis Plan (SAP). The SAP will be finalized before study database lock. The SAP will be available upon request.

It might have one interim analysis in the middle of the study on primary and secondary endpoints per the need decided by sponsor or authority. The proportion of incident and prevalent subjects will be tracked. The final analysis will be performed after end of the study which is the date the analytical dataset is completely available.

All background data such as patient demographics, PH group and indication-specific characteristics and prior or concomitant medication of PH, and concomitant diseases will be described by presenting frequency distributions and/or basic summary statistics.

Sample size and disposition information by analysis time point will be displayed in a frequency table.

6.7.2 Analysis of Treatment Data

Duration and dose of the Adempas[®] treatment during the observation period will be calculated for each patient. The dose will be displayed at the different visits/time windows. The number of patients adding and removing various PH medications (including Adempas[®]) will be summarized using frequency tables.

6.7.3 Analysis of Primary Outcome(s)

The main goal of this national registry is to assess the long-term safety of Adempas[®] in real life clinical use. Incidences of treatment-emergent adverse events, serious adverse events and all-cause mortality will be calculated, including adverse events of interest. An adverse event is considered as treatment-emergent when it has started or worsened after first dose of study medication after enrollment up to 2 days after end of treatment with study medication.

For the events, the 'raw' incidence proportion (regardless of the time each patient is treated), i.e. number of patients with events divided by the number of treated patients, will be presented as well as incidence rates, i.e. number of patients with events divided by the cumulative person-time on treatment (person-years) separately for incident and prevalent patients.

If the patient numbers allow, the statistics will be calculated for Adempas[®] and stratified for medically relevant subgroups, e.g.:

- Age
- Gender

MK-4836-001-01 FINAL PROTOCOL

- Aetiology (Nice Classification of PH)
- Hepatic impairment at baseline
- Renal impairment at baseline
- WHO functional class group at baseline
- According to e.g. 6 MWD thresholds \geq 380 m versus < 380 m at baseline
- Type of PH pre-treatment
- Concomitant medication use
- Systolic blood pressure at baseline
- Dosing level

A comprehensive list of medically relevant subgroups will be added to the SAP.

Tables which show the incidence proportion of adverse events overall and by MedDRA preferred term within the primary SOC will also be presented. Incidences of adverse events and serious adverse events starting more than 2 days after end of treatment will be tabulated separately.

